2. OBJECTIVES

Primary study objective:

To study effectivity of the epidural injection with analgesic and anti-inflammatory medication to relieve the symptoms within two weeks follow up.

It will be evaluated what the average leg pain score is in both treatment arms at two weeks follow up. It will be evaluated how long the effect lasts.

The leg pain and functionality at 4 weeks after randomization will also be evaluated to get informed on the responsiveness on TEI in a somewhat later stage.

Secondary study objectives:

To evaluate the outcome of TEI in the first two weeks after randomization as a predictor of NRS leg pain at 14-16 and ca 26 weeks after onset of leg pain.

Ideally, responsiveness to TEI can predict the clinical condition at 14-16 weeks after onset of sciatica. The hypothesis is that being non-responsive to TEI within two weeks, predicts an unsatisfactory condition after 14-16 weeks of suffering. This is the category of patients that in contemporary care in the Netherlands will be offered a surgical intervention. If our hypothesis is correct, in the future, this population of patients can be offered a surgical intervention at an earlier time point.

The ca 26-week time point is chosen since in the Sciatica trial [2], both the conservative and the surgical group demonstrated comparable outcome data.

Patients in this study are included while suffering from severe leg pain for 3-8 weeks.

Presumably most patients will enter the study with 4-6 weeks of leg pain. This means that on average 10 weeks after randomization, the 14-16 week leg pain time point is reached. This means that 21 weeks after randomization the ca 26-week leg pain time point is reached.

The response in NRS leg pain, ODI and patient satisfaction at 1 week after injection and at 2 weeks after injection will be correlated to the value of these parameters at 10 and 21 weeks after randomisation.

To evaluate the cost-effectivity of analgesic/anti-inflammatory epidural injections to relieve symptoms of early sciatica.

A substantial portion of the patients in this study will eventually have an MRI of the lumbar spine. These MRIs will be evaluated according to our standard MRI evaluation protocol, that has been proven to generate additional successful conclusions and subsequent publications in the past [10-15]. Protruding disc, disc and vertebral end plate changes (MODIC) will be correlated to clinical data.

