3. STUDY DESIGN

This is a prospective, open-label, randomized controlled trial on patients suffering from acute sciatica (3-8 weeks pain in the leg with a NRS ≥ 6) (see inclusion and exclusion criteria) in which consecutive patients who meet the inclusion criteria are invited to participate in the trial. The trial will take place at the Spaarne Gasthuis Hospital (SG) in Hoofddorp and Haarlem, the Netherlands in cooperation with researchers from Leiden University Medical Center (LUMC), Leiden, the Netherlands. Patient recruitment will occur at GP practices (GP collective Haarlemmermeer and Kennemerland, 185 GP's). The GP will diagnose the patient and, if the patient is diagnosed with sciatica, refer to the study investigator.

Eligible patients that are willing to participate are randomized to treatment with transforaminal epidural injections (treatment group) or standard conservative care (control group).

Randomization will take place using block randomization in a 1:1 allocation ratio. Patients from the treatment group will be treated with TEI, oral pain medication and, if deemed necessary by the GP, physiotherapy. The control group will only receive oral pain medication and if deemed necessary additional physiotherapy. For this study, the control group will not include placebo injections since we want to compare treatment with injections to treatment without injections. The focus will not be on the type of medication that is contained in the injection. Furthermore, a control group without injections will demonstrate what percentage of patients will experience spontaneous relief of symptoms (only using medication and/or physiotherapy) as it is known that in a significant part of the patients sciatica resolves without any intervention.

At baseline, clinical and demographic data are gathered for patients in both groups. Patients from the treatment group will receive TEI within 4 days after randomization. Patients from this group can receive multiple injections but an injection is only repeated after a certain interval time according to usual anaesthesiological guidelines. For all injections, details on timing, frequency and prevailing complications will be gathered.

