8.2 Secondary study parameter(s)

The absolute decline in NRS leg pain, NRS back pain and ODI and increase in EQ5D from baseline to 2 weeks after randomization will be calculated using t-tests. The same will be done for the baseline to 4 weeks after randomization time point (using t-tests).

Perceived recovery Likert data will be dichotomized (1 and 2 is success, 3-7 is no success) and compared at 2 and 4 weeks after randomization or injection and to 14 and 26 weeks after start of severe leg pain using Chi-square tests.

The 2-week success data will be correlated to the success data after 14 weeks and subsequently for 26 weeks using Chi-square tests to make predictions. Logistic regression analysis will be used to correlate 2-week (and 4-week) success data to the absolute data for NRS leg pain, NRS back pain, ODI, increase in EQ5D at 14 and 26 weeks.

Cost effectiveness analysis:

The economic evaluation will consist of a cost-effectiveness analysis from a healthcare perspective (CEA: costs per extra patient with symptom relieve, i.e. the primary outcome measure) and a cost-utility analysis from a societal perspective (CUA: costs per QALY). Both analyses will be trial-based, using patient reports, with a half-year time horizon. Healthcare use will be valued according to the Dutch guidelines. QALYs will be calculated as the area under the utility curve, estimated using the Dutch tariff for the EQ-5D. As sensitivity analysis, QALYs will also be calculated using the VAS for quality of life (with power transformation). Average costs and patient outcome will be compared according to intention-to-treat, using net-benefit analysis, and using multiple imputation to account for missing data.

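### Section 8.2 tests 2-week response as a predictor without an arm contrast, so a positive result could not separate information specific to TEI response from ordinary persistence of pain

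*Combined protocol and SAP*

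**What the plan says.** Section 2 (Objectives) sets the secondary aim: "To evaluate the outcome of TEI in the first two weeks after randomization as a predictor of NRS leg pain" at later time points. It states the hypothesis that "being non-responsive to TEI within two weeks, predicts an unsatisfactory condition after 14-16 weeks of suffering", and says that, if this is right, in future "this population of patients can be offered a surgical intervention at an earlier time point". The Summary likewise gives evaluating the injection as a predictor tool as part of the rationale. Section 2 maps the 14-16 week and 26-week points after onset to weeks 10 and 21 after randomisation.

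The analysis is in section 8.2: "2-week success data will be correlated to the success data after 14 weeks and subsequently for 26 weeks using Chi-square tests to make predictions". The next sentence adds: "Logistic regression analysis will be used to correlate 2-week (and 4-week) success data to the absolute data for NRS leg pain" and the other scores. Section 2 also says that response, including "patient satisfaction at 1 week after injection and at 2 weeks after injection will be correlated to the value of these parameters" at weeks 10 and 21.

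None of these sentences says which arm is analysed. None mentions a parallel estimate in controls, an interaction or adjustment for baseline pain. Section 3 does give the controls a relevant role, "a control group without injections will demonstrate what percentage of patients will experience spontaneous relief of symptoms", but no section carries it into the prediction analysis.

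**The concern.** Someone who still has leg pain at week 2 is more likely to have it at week 10, injected or not. An association between early and later status is therefore expected in both arms. The hypothesis, however, credits the information to response to TEI. To support that, the association has to be stronger after TEI than after two weeks of conservative care alone, and the planned tests do not make that comparison.

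At stake is how a positive finding would be read. It could be presented as evidence that the injection works as a predictor, with the consequence for surgical timing that section 2 mentions, when the same association may be present in patients who had no injection. A chi-square p-value also gives no predictive value. The underlying 2x2 table would yield one, but section 8.2 does not commit to reporting it.

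**Working it through.** **Plan's own figure.** Section 4.4: difference 1.5, SD 2.6, power 90%, two-sided 5%. n per arm = 2 × (1.960 + 1.282)² × 2.6² / 1.5² ≈ 63.1, so 64 (exact t-test 64.1). 128 / 0.9 = 142.2. The stated 64, 128 and 142 reproduce. They size the primary comparison; no figure is given for the prediction analysis.

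**Simulation inputs.**
- From the documents: 64 evaluable patients per arm, week-2 mean NRS 4.0 (TEI) and 5.5 (control), SD 2.6 (section 4.4); success is NRS below 4 (section 3).
- Assumed: bivariate normal scores rounded and limited to 0-10, week-10 mean 3.5 and SD 2.6 in both arms, and the same week-2/week-10 correlation in both arms. Equal correlation means that TEI response tells no more than ordinary persistence does.

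**Share of trials with p < 0.05.**

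| Correlation | Chi-square, TEI arm | Chi-square, control arm |
|---|---|---|
| 0.3 | 34% | 27% |
| 0.4 | 56% | 46% |
| 0.5 | 76% | 66% |
| 0.6 | 91% | 83% |

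Pooling the arms gives 52% to 99% over this range. The between-arm contrast of log odds ratios (the arm by week-2 success interaction) rejects in about 3% to 4%. At correlation 0 the TEI-arm chi-square rejects in about 5%.

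**Sensitivity.** With unrounded scores and a later mean of 3.0 in both arms, the TEI-arm figure is 17% at correlation 0.2, 54% at 0.4, 90% at 0.6 and 98% at 0.7. Pooled, it is 78% at 0.4. The interaction rejects in 1% to 4% over correlations 0.2 to 0.7.

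**Number of week-2 non-successes.** With integer scores, NRS of 4 or more corresponds to an underlying value of at least 3.5. TEI arm: P = Φ((4.0 − 3.5)/2.6) = Φ(0.19) ≈ 0.58, and 0.58 × 64 ≈ 37. Control arm: Φ((5.5 − 3.5)/2.6) = Φ(0.77) ≈ 0.78. If, for illustration, 26 of 37 TEI non-successes were also unsatisfactory later (70%), the Wilson 95% CI would be 54% to 83%.

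**Predictive values under equal persistence.** The probability of later NRS of 4 or more, given week-2 NRS of 4 or more, is 64% (TEI) versus 58% (control) at correlation 0.5, and 67% versus 59% at 0.6. The same cut-off selects 58% of one arm and 78% of the other, so predictive values differ although persistence does not.

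**Power of the interaction (correlations 0.7 in TEI, 0.4 in control).** Dichotomised, by simulation with later mean 3.0: about 20% (odds ratios about 9 versus 3). Continuous, by Fisher z: (0.867 − 0.424) / √(2/61) = 0.444 / 0.181 = 2.45, and Φ(2.45 − 1.96) ≈ 0.69. With equal SDs a slope equals the correlation, so 69% approximates the power of a slope interaction before baseline adjustment.

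**The case against.** The strongest reply is that the hypothesis can be read prognostically: among treated patients, those with a poor week 2 tend to have a poor week 10. That statement needs no control arm, and the planned tests can support it. This stands. It does not cover the wording of the Summary and section 2, which attach the information to the injection.

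A reader might infer that the plan would confirm its hypothesis even if week-2 status carried no information at all. It would not: at correlation 0 the chi-square holds about 5%. The 34% to 91% are correct rejections of independence, and the difficulty lies in attributing them to TEI.

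A reader might also infer that the control arm is excluded. Section 8.2 is silent on this. TEI-only and pooled analysis are both possible, and neither contrasts the arms.

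One might take the 33% non-responders cited in section 1 and expect 0.33 × 64 ≈ 21 patients. The response rate given there for the cited study is for response within hours of injection, not NRS below 4 at two weeks, and section 4.4's own inputs imply about 37.

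Finally, the interaction conditions on a status reached after randomisation, so it is not a randomised comparison, and its power is low. Both points hold. They argue for an exploratory label and continuous scores; they do not make the chi-square an answer to the question.

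**Conclusion.** The concern holds in this form: section 8.2 as written can show that week-2 pain is prognostic, but cannot show that response to TEI carries information beyond ordinary persistence. Under equal persistence the TEI-arm test would be significant in about 34% to 91% of trials for correlations of 0.3 to 0.6. That range rests on a correlation and a later mean that the documents do not give, and on success meaning NRS below 4. Section 8.2 also defines success on the Likert scale, immediately before the sentence at issue.

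This is a secondary objective. The primary comparison is unaffected, and section 2 makes earlier surgery conditional on the hypothesis being correct. The change should still be made, because following the plan exactly leaves the stated question unanswered. One limit remains under any analysis: section 3 links week-2 pain to eligibility for surgery, and the prediction analysis does not say how later scores after surgery are handled.

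**What to change.** In section 8.2, for weeks 10 and 21 separately:

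1. Model later NRS leg pain on arm, week-2 NRS (preferably continuous), their interaction and baseline NRS, using both arms, with week 2 counted from randomisation so that it means the same in each.
2. Report the week-2/later association per arm with 95% CIs. Credit information to TEI response only through the interaction estimate and its CI, labelled exploratory.
3. Report positive and negative predictive values per arm with 95% CIs as description only. They should not be the between-arm criterion, since they differ whenever the week-2 distributions differ.
4. If the chi-square and logistic regression are kept, state which arm or arms they use and that they address prognosis only.

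Cost: wording and one model per time point. Sections 6.1.1 and 6.3 already schedule the needed scores in both arms. The downside is an imprecise interaction and therefore a more modest conclusion.

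### The prediction objective is tested for association only: section 8.2 plans no predictive value or confidence interval for 2-week non-response

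*Combined protocol and SAP*

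**What the plan says.** Section 2 (Objectives) states the hypothesis as a prediction for patients: "The hypothesis is that being non-responsive to TEI within two weeks, predicts an unsatisfactory condition after 14-16 weeks of suffering". It adds that, if this is correct, in future "this population of patients can be offered a surgical intervention at an earlier time point". It also names the early measures to be analysed: "The response in NRS leg pain, ODI and patient satisfaction at 1 week after injection and at 2 weeks after injection". Of these measures it says that they "will be correlated to the value of these parameters at 10 and 21 weeks after randomisation". The same section equates 10 and 21 weeks after randomisation with about 14-16 and 26 weeks after onset.

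Section 8.2 turns this into two analyses. The first sets 2-week success against later success, at 14 weeks to begin with, then "subsequently for 26 weeks using Chi-square tests to make predictions". The second is a regression: "Logistic regression analysis will be used to correlate 2-week (and 4-week) success data to the absolute data for NRS leg pain", and likewise for back pain, ODI and EQ-5D at 14 and 26 weeks.

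For this predictor, section 8 names no predictive value, sensitivity, specificity, discrimination measure or confidence interval, and sets no minimum useful value. The one percentage of correct prediction it does plan (section 8.3) compares the clinical diagnosis with the MRI level, which is a different question.

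**The concern.** Whether non-response could inform an earlier offer of surgery depends on two figures: the proportion of non-responders who are unsatisfactory later, and how precisely the trial estimates it. A chi-square p-value answers a weaker question, namely whether that proportion differs from the one among responders. Two proportions can differ clearly while the one that matters stays near or below one half.

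The other planned analyses do not close the gap. The logistic regression has the early result as its binary variable and links it to later continuous scores. The correlation in section 2 describes strength of association. Neither yields the probability of a poor later condition given early non-response. In addition, the week-1 response that section 2 undertakes to use does not appear in section 8.2, where the prediction analyses take the early response only as success or no success at week 2 (and week 4).

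At stake is how the secondary result will be read: a significant test could be reported as successful prediction when the predictive value is modest and imprecise.

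**Working it through.** **Stated size.** The only sample size is for the primary t-test (section 4.4): difference 1.5, SD 2.6, power 90%, 5% significance. This reproduces at 64 per group, and 128/0.9 = 142.2, stated as 142, or 71 per arm. No size or target value is given for the prediction objective.

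**Inputs for the illustration**
- TEI arm: 142/2 = 71.
- Non-responders: one third, 71/3 ≈ 24, leaving 47 responders. The 33% is the average that section 1 takes from a cited study.
- Responders unsatisfactory later: 20%, 30% or 40%, i.e. 9, 14 or 19 of 47. This is an assumption; the documents give no figure.
- Test: Pearson chi-square without continuity correction, also an assumption, since section 8.2 does not specify.

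**Formulas.** Let a and b be the unsatisfactory and satisfactory non-responders, and c and d the same for responders.
- X² = N(ad − bc)² / [(a+b)(c+d)(a+c)(b+d)]
- Positive predictive value (PPV) = a/(a+b), with Wilson 95% CI: [p + z²/2n ± z√(p(1−p)/n + z²/4n²)] / (1 + z²/n)

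**Middle case, 13/24 against 14/47**
- ad − bc = 13×33 − 11×14 = 429 − 154 = 275
- X² = 71×275² / (24×47×27×44) = 5,369,375 / 1,340,064 = 4.007, p = 0.045
- 12/24 is not significant (X² = 2.80), so 13 is the smallest count that is.
- PPV = 13/24 = 54%. Wilson: (0.5417 + 0.0800 ± 1.96×0.1096)/1.1601 gives 35-72%.
- Negative predictive value (NPV) = 33/47 = 70%; sensitivity = 13/27 = 48%; specificity = 33/44 = 75%.

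**Smallest significant result by assumption**

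| Responders unsatisfactory | Non-responders unsatisfactory | p | PPV (95% CI) | Flagged but satisfactory |
|---|---|---|---|---|
| 9/47 | 10/24 | 0.043 | 42% (24-61%) | 14/24 = 58% |
| 14/47 | 13/24 | 0.045 | 54% (35-72%) | 11/24 = 46% |
| 19/47 | 16/24 | 0.036 | 67% (47-82%) | 8/24 = 33% |

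In every row the lower confidence limit is below 50%.

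**Sensitivity to the assumptions**
- *Choice of test.* On the 13/24 table the continuity-corrected p is 0.081 and Fisher's exact p is 0.070. With the correction, 14/24 is needed: PPV 58% (CI 39-76%).
- *Share flagged.* Section 3 defines success as NRS leg pain below 4, and section 4.4 expects a TEI mean of 4.0. If scores are roughly normal, about half the arm (36 of 71) is flagged. Then 20/36 against 11/35 gives X² = 71×(20×24 − 16×11)² / (36×35×31×40) = 6,561,536 / 1,562,400 = 4.20, p = 0.040 uncorrected, with PPV 56% (CI 40-70%).
- *Evaluable patients.* With 64 in the arm (21 non-responders, 43 responders), 12/21 against 13/43 suffices: PPV 57% (CI 37-76%).
- *Precision at a high value.* Even 17/21 (81%) has a CI of 60-92%.

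**The case against.** The strongest reply is that little is lost. The objective is secondary, the primary t-test and the sample size are untouched, and the planned 2x2 table already holds the counts for every predictive measure. The chi-square test is also not the whole plan, since a logistic regression and a correlation accompany it. All of this stands, and it limits the weight of the point. It does not remove it: those analyses also give association only, and a measure or threshold chosen after the data are seen carries less credibility than one fixed beforehand.

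A second reply is that the 33% comes from a study in which response was judged within hours of injection, whereas this trial judges it at two weeks. That is correct. The calculation with about half the arm flagged shows that the conclusion does not depend on it.

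Two stronger readings are tempting but unsupported. A reader might infer that nearly half of the flagged patients would recover without surgery. The 46% is one assumed case at the significance boundary. Moreover, section 3 allows an operation before 14-16 weeks, so a satisfactory later score may follow surgery. A reader might also infer that p<0.05 triggers earlier surgery. The documents state no such rule: section 2 is conditional and looks to the future, and section 10.6 offers guideline authors the trial's results in general, not this one.

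**Conclusion.** The point holds as a should-fix on a secondary objective. The hypothesis concerns what happens to non-responders, and none of the planned analyses reports that proportion or its precision. Under the assumptions shown, significance can be reached at a PPV of 42-67%, with one third to over half of the flagged patients satisfactory at follow-up. The size is illustrative: it moves with the share flagged, the responders' outcome rate and the version of the test. The direction does not: in each boundary case worked above, the interval for the PPV is wide and its lower limit is below 50%.

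Two gaps make the planned table itself ambiguous. Section 8.2 does not say whether success in the prediction table means NRS leg pain below 4 (section 3) or Likert 1-2 (defined in section 8.2), nor whether the table uses the TEI arm alone.

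**What to change.** In section 8.2:
- Make the main prediction result the PPV of 2-week non-response for an unsatisfactory condition at week 10 (and week 21) in the TEI arm. Report NPV, sensitivity and specificity with it, all with 95% CIs, from the 2x2 table already planned. The chi-square test may stay as supportive.
- Use one success definition throughout: either NRS leg pain below 4 or Likert 1-2.
- State how patients operated on before the outcome time point are counted.
- Set, before analysis, the lowest lower confidence limit of the PPV at which prediction will be concluded.
- Optionally, add an exploratory model with continuous NRS leg pain and ODI at weeks 1 and 2, which would also honour the week-1 analysis announced in section 2.

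The cost is SAP wording only, because NRS leg pain and ODI are already collected at weeks 1, 2, 10 and 21. The downside is presentational: the result will look less decisive than a p-value, and with about 21-36 flagged patients the intervals will be wide.
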